11.2.2 SAEs (Including Deaths) and Adverse Events Leading to Study Drug Discontinuation

SAEs and AEs leading to Depatux–M/Placebo and TMZ discontinuation, dose reduction and dose interruption, and death will be summarized separately by SOC and PT in each treatment arm. Separate listings for SAEs, AEs leading to death and AEs leading to treatment discontinuation will also be provided.

11.2.3 Listing of Adverse Events

The following additional summaries of adverse events will be prepared.

- Listing of treatment-emergent serious adverse events.
- Listing of treatment-emergent adverse events that led to discontinuation of study drug.
- Listing of treatment-emergent fatal adverse events.
- Listing of Grade 3 or higher adverse events

11.3 Analysis of Depatux-M targeted ophthalmologic exam (TOE) results

The following assessments from the TOE will be analyzed using shift table for each treatment arm, separately.

- Visual acuity (20/10 - 20/20, 20/25 - 20/40, 20/50 - 20/100, 20/125 - 20/160, 20/200 OR worse) – Best eye and worst eye separately
- Microcysts/Edema (None/Trace/Mild/Moderate/Severe) – Worst eye
- Superficial Punctate Keratopathy (None/Trace/Mild/Moderate/Severe) – Worst eye
- Photophobia (None/Mild/Moderate/Severe) – Worst eye
- Eye Pain (Yes /No) – Worst eye

For each of the endpoints above, summary tables and shift tables will be created for the timepoints:

For all subjects in the safety population:

- baseline value
- worst value in chemo-radiation phase
- worst value in whole study
- final value on treatment (up to 49 days after last dose)
- last value in follow-up

For subjects who received at least one adjuvant dose of any study treatment:

- baseline value
- worst value in chemo-radiation phase
- last value in chemo-radiation phase
- worst value in adjuvant phase
- final value in adjuvant phase (up to 49 days after last dose)
- last value in follow-up

Data will be summarized by n (%) by severity level at each of the above timepoints. Shift tables will be produced for baseline to post-baseline timepoint for each of the endpoints above.

Chemo-radiation phase is defined as from the Study Rx Day 1 to the day before the first adjuvant dosing. If adjuvant dosing is missing then, last Depatux-M/Placebo dosing + 49 days would be the end date of chemo-radiation phase. Adjuvant phase is defined as day of first adjuvant dosing to the last Depatux-M/Placebo dosing + 49 days. Follow-up phase starts after last Depatux-M/Placebo dosing + 49 days to the study completion.

In addition, selected continuous TOE endpoints will be summarized for change from baseline.

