The dose-limiting toxicities (DLTs) observed after ABT-414 exposure have been limited to manifestations from the formation of corneal deposits related to cys-mcMMAF, a syndrome hereafter referred to as microcystic keratopathy. This is thought to be a result of damage directly to the transient amplifying cells of the limbus, cells that differentiate and give rise to the corneal epithelium. However, with the exception of these ocular adverse events, as described in detail below, adverse events reported were usually Grade 1 or 2, infrequent, and more likely related to the underlying cancer, concomitant chemotherapy or chemoradiotherapy. DLTs for all groups in both studies were comprised of a variety of different preferred terms for eye-related signs (including keratitis, corneal cysts, corneal deposits, ocular hyperemia) and symptoms (most commonly vision blurred, photophobia, dry eye, eye pain, foreign body sensation in eyes, and lacrimation increased). Similar findings have been reported for other ADCs utilizing the cys-mcMMAF toxin.⁴ Given that the cornea regenerates every 3 – 4 weeks, to date, all cases of microcystic keratopathy have resolved without long-term sequelae after drug discontinuation. Both the incidence and severity of eye toxicity appear to be dose-related. While ABT-414 dose reduction for subjects with high-grade toxicities generally reduces symptom severity and allows for continued dosing, the overall incidence rate remains very high at the recommended Phase 2 doses proposed for further clinical studies.

The microcystic keratopathy noted in Study M12-356 is similarly described with other chemotherapy agents, including high-dose cytarabine. Prophylactic steroid eye drops are routinely used to control these symptoms. Thus, prophylactic steroid ophthalmologic solution was administered to subjects in Study M12-356 once ocular toxicities were observed. One subject in Study M12-356 who had stopped ABT-414 treatment due to a Grade 3 eye toxicity at the 1.0 mg/kg level without steroid ocular prophylaxis was able to tolerate the same 1.0 mg/kg dose level when ABT-414 was restarted along with steroid prophylaxis. Based on this and other experiences, ocular steroid prophylaxis is indicated for all subjects receiving ABT-414 treatment at dose levels of 1.0 mg/kg and above.

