The start of the first cycle during the Adjuvant Therapy Phase will be scheduled approximately 28 days after the last day of radiotherapy. During the Adjuvant Therapy Phase, all subjects will receive oral TMZ 150 – 200 mg/m² once daily on Days 1 – 5 of each 28-day cycle for 6 cycles unless there is disease progression, unacceptable toxicity, or other reasons to discontinue. Subjects in Arm A will receive blinded ABT-414 1.25 mg/kg by intravenous infusion on Day 1 and Day 15 of each 28-day cycle for 12 cycles. Subjects in Arm B will receive blinded placebo IV infusion on Day 1 and Day 15 of each 28-day cycle for 12 cycles.

If after completing 12 cycles of adjuvant treatment, the subject is tolerating study drug (ABT-414 or placebo) and the Investigator believes the subject is continuing to benefit from ongoing study drug treatment, the Investigator may extend the Adjuvant Phase after consultation with the Neuro-Medical Oncology Chair or AbbVie Medical Monitor, as long as disease progression has not been determined.

Occurrence of disease progression to calculate PFS will be determined by the Investigator, based on local evaluation of images and other clinical information using the Response Assessment in Neuro-oncology (RANO) criteria ([Appendix I](#)). Post-baseline scans will be obtained \leq 14 days before Day 1 of each odd-numbered cycle (Cycles 1, 3, 5, etc.) of the Adjuvant Phase and \leq 14 days before each visit (approximately every 8 weeks) of the Follow-Up Phase. MR images will also be reviewed centrally by an independent blinded reviewer for radiographic evidence of disease progression. When study drug (ABT-414/placebo) is discontinued for any reason, a Final Study Drug Visit will be conducted. All subjects will have a 35-Day and 49-Day Follow-Up Visit (\pm 3 days) after the last dose of ABT-414/placebo. The 49-Day Follow-Up

Visit will focus on evaluation of ongoing adverse events. Overall survival will be assessed quarterly after study discontinuation.

Neurocognitive testing and patient-reported outcomes will be assessed approximately every 8 weeks during the Adjuvant and Follow-Up Phases, and then at disease progression.

Table 1. Study Activities – Chemoradiation Phase	Screening ^a		Chemoradiation Phase ^b						
	Screening 1	Screening 2	Day 1 Wk 1 (Fraction 1 of RT)	Day 1 of Wk 2	Day 1 of Wk 3	Day 1 of Wk 4	Day 1 of Wk 5	Day 1 of Wk 6	Day 1 of Wk 7
Informed Consent	X								
Medical and Oncologic History		X							

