- c. As per TMZ prescribing information, during the 28-day cycle of TMZ, a blood count for ANC and platelets should be performed 21 days (\pm 2 days) after the start of each TMZ cycle. If the ANC falls below 1,500/ μ L or if the platelet count falls below 100,000/ mm^3 , then blood counts should be performed weekly until recovery to these levels before TMZ dosing. A certified local lab may be used instead of central lab; if so, ANC and platelet results should be reported in the eCRF. Day 22 testing may be omitted for cycles in which TMZ is not administered or if local prescribing information allows for a different testing schedule for ANC and platelets.
- d. Final Study Drug Visit to be performed approximately 14 days after last dose of ABT-414/placebo. The physical examination and MR imaging from the first visit of the Follow-Up Phase will be used for the Final Study Drug Visit if these visits coincide (e.g., if the subject completes 12 cycles of Adjuvant Phase).
- e. To be performed 35 days (\pm 3 days) after the last dose of study drug (placebo or ABT-414). If the Final Study Drug Visit is more than 35 days after the last dose of study drug, then 35-day safety follow-up procedures will not be performed.
- f. Visits in Follow-Up Phase to occur every 8 weeks, beginning 8 weeks after Day 1 of the last odd-numbered cycle in the Adjuvant Phase.
- g. Height will be assessed at Screening only. Weight will be collected at all visits. Complete physical examination will be performed at Screening only. Symptom directed physical examination will be performed at all other designated visits as clinically indicated.
- h. Ophthalmology exam to be performed prior to ABT-414/placebo dosing on Day 1 (or up to 7 days prior to Day 1) of Cycle 1, Cycle 2, and every odd-numbered cycle thereafter (Cycles 3, 5, 7, etc.). Ophthalmology exam for Cycle 1 Day 1 may be omitted if the subject had no corneal microcysts or ocular adverse events during or after the Chemoradiation Phase. Ophthalmology exams may be discontinued if the subject has been on Level 1 eye drops with no ocular toxicity for 2 consecutive eye exams.
- i. Ophthalmology exam at Day 35 Follow-Up Visit to be done only if subject had corneal microcysts or other ocular findings related to ABT-414 or ocular steroids on previous exam and repeated at least every 8 weeks until satisfactory resolution of eye toxicities.

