Additional eye exams may be performed as needed throughout the study, including additional exams if evidence of microcystic keratopathy persists after the 35-Day Follow-Up Visit to monitor reversibility. A subset of sites will be asked to provide ophthalmic photography (e.g., slit lamp, confocal microscopy, Heidelberg Retina Tomographer [HRT3], etc.) of corneal abnormalities.

Ophthalmologic exams may be discontinued for subjects who have no evidence of eye toxicity on 2 consecutive examinations after being decreased to Level 1 eye drops.

Qualified medical personnel will perform the ophthalmologic examination, which will include assessments of visual acuity, intra-ocular pressure, funduscopy examination (at Screening, 35 Day Follow-Up Visit only), and slit lamp examination according to standard procedures of the ophthalmologist. The corneas will be evaluated via slit lamp at every exam to identify potential pathological changes. Grading on the ABT-414-TOE findings for "microcysts/edema" and "superficial punctate keratopathy" will be used to inform potential changes in the level of prophylactic steroid eye drops to be used with ABT-414/placebo dosing, as described in Section 5.5. Grading for these two items is as follows:

Microcysts/Edema

0	=	None
+0.5 (Trace)	=	Trace, localized epithelial haze
+1 (Mild)	=	Dull glass appearance that may include fine individual microcystic changes
+2 (Moderate)	=	Dull glass appearance of epithelium with large number of vacuoles with or without stromal edema
+3 (Severe)	=	Epithelial bullae and/or whorl keratopathy, localized or diffuse, with or without stromal striae

Superficial Punctate Keratopathy

0	=	None
+0.5 (Trace)	=	Trace (1 – 5 puncta)
+1 (Mild)	=	Mild (6 – 20 puncta)
+2 (Moderate)	=	Moderate (> 20 puncta, but countable)
+3 (Severe)	=	Severe (too many puncta to count)

Table 4: Ophthalmology Examination Schedule

STUDY VISIT/PERIOD*	EXAM REQUIRED?	COMMENTS
Screening	Yes	Establishes baseline assessment for corneal exam and visual acuity
Chemoradiation Phase		
Day 1, Week 5 (≤ 7 days before Week 5 ABT-414/placebo dose)	Yes	Do not decrease Level of eye drops until after the subject has received at least 2 eye exams
Day 1, Week 7 (7 – 14 days after Week 5 ABT-414/placebo dose)	Yes	--
Recovery Period		
No ophthalmology exam required	No	As-needed basis only
Adjuvant Phase		
Day 1, Cycle 1**	No	Exam not required if the subject had no corneal microcysts or ocular adverse events during or after the Chemoradiation Phase

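### The SAP's eye-exam tables class the Day-35 off-drug exam as on-treatment, and corneal reversibility cannot be read from them

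*SAP*

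**What the plan says.** SAP 11.3 plans summary and shift tables for visual acuity, microcysts/edema, superficial punctate keratopathy, photophobia and eye pain. For the whole safety population one row is the "final value on treatment (up to 49 days after last dose"); for subjects dosed in the adjuvant phase the matching row is the "final value in adjuvant phase (up to 49 days after last dose"). Both tables also have worst-value rows and a last value in follow-up, with follow-up defined as: "Follow-up phase starts after last Depatux-M/Placebo dosing + 49 days to the study completion". Results are n (%) at each timepoint, and shifts run from baseline to each later timepoint.

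Protocol Section 4.1 states: "All subjects will have a 35-Day and 49-Day Follow-Up Visit", each with a 3-day margin. Table 2 there schedules eye exams at Cycle 2, at odd-numbered cycles and at the 35-day visit. It has none at the Final Study Drug Visit and none at Day 49. Note i to that table reads: "Ophthalmology exam at Day 35 Follow-Up Visit to be done only if subject had corneal microcysts or other ocular findings related to ABT-414" or to ocular steroids, with repeats at least every 8 weeks until satisfactory resolution. Section 4.2 and Table 4 list the Day-35 exam without that condition. Section 4.2 also allows as-needed exams, including "additional exams if evidence of microcystic keratopathy persists after the 35-Day Follow-Up Visit to monitor reversibility".

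**The concern.** Corneal toxicity is the characteristic harm of this drug, and the protocol leans on its being reversible: in Section 1.0 ("Given that the cornea regenerates every 3 – 4 weeks", all cases are said to have resolved after stopping), in Section 5.12.4, and in Section 8.1.2.3 on what subjects are told. The interim results in Section 1.0 give corneal adverse events of Grade 3 or higher in 61.0% of the ABT-414 arm and 0.6% of the placebo arm. The targeted eye exam is the objective record against which reversibility can be checked.

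If an exam done weeks after stopping is labelled on-treatment, a reader cannot tell a mild end-of-treatment finding from a worse one that has healed. If the follow-up row comes mostly from patients not yet healed at Day 35, its percentages do not describe affected patients as a whole. What is at stake is a plain safety question: of those with a corneal finding, how many recovered after stopping?

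**Working it through.** **1. Where the Day-35 exam falls.** Inputs: visit at 35 ± 3 days (Protocol 4.1); cut at 49 days (SAP 11.3); reversal after 4 to 6 weeks off drug (Protocol 1.0 and 5.12.4).

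- Visit window: 35 − 3 = 32 to 35 + 3 = 38 days.
- Distance inside the cut: 49 − 38 = 11 to 49 − 32 = 17 days. The exam is always classed on-treatment or adjuvant-phase.
- Reversal period: 4 × 7 = 28 to 6 × 7 = 42 days. The window of 32 to 38 days lies wholly inside it.

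**2. Day 35 is the usual source of the final value.** With no eye exam at the Final Study Drug Visit, the next scheduled exam after the last odd-cycle one is Day 35. Under Table 2 note i only patients with earlier findings have it. Clear patients would then contribute a pre-dose value and affected patients a recovery value. Section 1.0 reports corneal adverse events in 94.7% versus 36.1%. Those are adverse-event rates, not exam findings, but they suggest that the mixture would differ by arm. Under Section 4.2 and Table 4 everyone has the exam, and the row is then largely off-drug.

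**3. No other planned row isolates Day 35.** The SAP visit windows for laboratory values (7.5.2, Table 3) and for vital signs and KPS (7.5.3, Table 5) each have a 35-day follow-up row. The eye-exam windows (7.5.4, Tables 6 and 7) have none.

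**4. Who enters the follow-up row.** The next repeat under note i is due by 32 + 56 = Day 88 to 38 + 56 = Day 94, after follow-up opens on Day 50. Exams after Day 35 are driven mainly by persisting findings, with as-needed exams possible.

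**5. Effect on the follow-up percentages (assumed rates).** Take 100 patients with a finding at the last on-drug exam. Let a be the share clear at Day 35 and b the share of the rest who clear later. Assume that all patients still abnormal at Day 35, and no others, are examined after Day 49. The row holds 100(1 − a) patients. Over examined patients it shows 1 − b unresolved; over all affected patients the figure is (1 − a)(1 − b). For b < 1 the ratio is 1/(1 − a), whatever b is.

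| a | b | n in row | Unresolved, of examined | Unresolved, of all affected | Ratio |
|---|---|---|---|---|---|
| 0.2 | 0.8 | 80 | 16/80 = 20% | 16% | 1.25 |
| 0.5 | 0.8 | 50 | 10/50 = 20% | 10% | 2 |
| 0.8 | 0.5 | 20 | 10/20 = 50% | 10% | 5 |
| any of these | 1 | 100(1 − a) | 0% | 0% | – |

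The documents give neither a nor b for this trial.

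**6. What else could answer the question.** Worst and last values are each tabulated but not crossed. SAP 11.2.1 plans time to onset of corneal events and nothing on time to resolution.

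**The case against.** The strongest reply is that nothing is hidden. The 49-day window is printed in the row label and matches the study-wide safety convention (treatment-emergent definition, adverse-event collection, hepatic laboratory criteria). Worst values are shown for each phase and for the whole study. A patient healed by Day 35 appears as healed in the final-value row, so recovery is spread over two labelled rows and not lost. Reversibility is not a listed objective or safety endpoint. All of this stands, and it rules out calling the results misreported. It does not remove the mixture: SAP 11.1 exempts the eye exam from the treatment-emergent restriction, so the convention does not force the 49-day cut here.

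A reader might also infer that the follow-up row holds only unresolved cases. The documents do not support that. The tabulated value is the last one, note i continues exams until satisfactory resolution, and as-needed exams can add other patients. Selection acts on status at Day 35, not on the final status.

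The denominator argument stands too. SAP 11.3 heads the list with the safety population and does not say that percentages are over examined patients. With a safety-population denominator the inflation in step 5 does not arise, although unexamined patients then need a category of their own.

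**Conclusion.** The point holds as a cheap improvement. By date arithmetic alone, under either version of the Day-35 rule, SAP 11.3 labels an exam about 5 weeks off drug as on-treatment. The follow-up row covers mainly patients still abnormal at Day 35, without a stated denominator, and is shifted only against baseline. Together the planned tables do not yield the share of affected patients who recovered.

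The size is open. The factor 1/(1 − share clear at Day 35) applies only under an examined-only denominator. A reader who assumes that 50% to 90% are clear at Day 35 would arrive at a 2- to 10-fold overstatement, but those rates are not in the documents; at 20% it is 1.25-fold. Nor is 94.7% of the ABT-414 arm a suitable base for counting affected patients: it is any-time incidence of a broad event group that includes dry eye, blurred vision and eye pain.

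**What to change.** In SAP 11.3:

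1. Report the last eye exam up to the last dose of Depatux-M/placebo separately from post-dose exams, and give the Day-35 exam its own row, as for laboratory values and vital signs.
2. Add a shift from the worst post-baseline value to the last available exam at any time, including Day 35 and later as-needed exams.
3. Among all subjects with a post-baseline corneal finding, report by arm n (%) resolved, unresolved and not re-examined, with that full group as denominator. The third category is needed: Protocol Appendix X says targeted eye-exam data will not be collected for those of the approximately 48 subjects still on ABT-414 who continue.

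Keep the worst-value rows. The last on-drug exam can predate the final doses: with a last dose on Cycle 6 Day 1, the preceding scheduled exam is at Cycle 5 Day 1 or up to 7 days before it, which is 28 to 28 + 7 = 35 days earlier. For the same reason a window tied to the Final Study Drug Visit (about Day 14) would add little, since no eye exam is scheduled there.

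Protocol Table 2 note i and Section 4.2/Table 4 must be reconciled on whether the Day-35 exam is conditional, because that decides who contributes to each row.

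Cost: SAP wording, a changed row definition and one extra table, from data already collected.

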11.4 Analysis of Laboratory Data

The hematology and clinical chemistry lab parameters listed in [Table 8](#) are planned to be collected for each subjects at baseline and scheduled post-baseline visits. The urinalysis lab parameters are planned to be collected at baseline only.

Table 8. Clinical laboratory test

Hematology	Clinical Chemistry	Urinalysis
Hematocrit	Blood urea nitrogen (BUN)	Specific gravity
Hemoglobin	Creatinine	Ketones
Red blood cell (RBC) count	Total bilirubin	pH
White blood cell (WBC) count	Serum glutamic-pyruvic transaminase (SGPT/ALT)	Protein
Neutrophils	Serum glutamic-oxaloacetic transaminase (SGOT/AST)	Blood
Bands (if detected)	Alkaline phosphatase (ALP)	Glucose
Lymphocytes	Gamma-glutamyl transferase (GGT)	Microscopic examination if dipstick results are positive
Monocytes	Sodium	
Basophils (if detected)	Potassium	
Eosinophils (if detected)	Calcium	
Absolute platelet count	Inorganic phosphorus	
Mean corpuscular volume (MCV)	Glucose	
Coagulation (screening Only)	Cholesterol	
Prothrombin time	Triglycerides	
Activated PartialThromboplastin Time (aPTT)	Total protein	
International normalized ratio (INR)	Uric Acid	
	Albumin	
	Lactate dehydrogenase (LDH)	
	Magnesium	
	Chloride	
	Bicarbonate	

11.4.1 Variables and Criteria Defining Abnormality

NCI CTCAE v. 4 grading criteria for laboratory abnormalities are shown in [Table 9](#) and [Table 10](#).

Table 9. Criteria for NCI CTCAE Grades for Laboratory Values Hematology Variables

	Units	NCI CTCAE Grade ≥ 3		NCI CTCAE Grade ≥ 4	
		Low	High	Low	High
Hematology Variables					
Hemoglobin	g/L	< 80	> ULN + 40		
White blood cell count	$10^9/L$	< 2		< 1	
Neutrophil count	$10^9/L$	< 1		< 0.5	
Lymphocyte count	$10^9/L$	< 0.5		< 0.2	
Absolute Platelet count	$10^9/L$	< 50		< 25	
Coagulation Variables					
INR increased	ratio		> $2.5 \times \text{ULN}^*$		

* Or baseline if on anticoagulation.

Table 10. Criteria for NCI CTCAE Grades for Laboratory Values - Chemistry Variables

Chemistry Variables	Units	NCI CTCAE Grade ≥ 3		NCI CTCAE Grade ≥ 4	
		Low	High	Low	High
Creatinine	mcmol/L		$> 3 \times \text{ULN}$		$> 6 \times \text{ULN}$
Total bilirubin	mcmol/L		$> 3 \times \text{ULN}$		$> 10 \times \text{ULN}$
Alanine aminotransferase (ALT/SGPT)	U/L		$> 5 \times \text{ULN}$		$> 20 \times \text{ULN}$
Aspartate aminotransferase (AST/SGOT)	U/L		$> 5 \times \text{ULN}$		$> 20 \times \text{ULN}$
Alkaline phosphatase (ALP)	U/L		$> 5 \times \text{ULN}$		$> 20 \times \text{ULN}$
Gamma glutamyl transferase (GGT)			$> 5 \times \text{ULN}$		$> 20 \times \text{ULN}$
Sodium	mmol/L	< 130	> 155	< 120	> 160
Potassium	mmol/L	< 3	> 6	< 2.5	> 7
Calcium	mmol/L	< 1.75	> 3.1	< 1.5	> 3.4
Glucose	mmol/L	< 2.2	> 13.9	< 1.7	> 27.8
Cholesterol	mmol/L		> 10.34		> 12.92
Triglycerides	mmol/L		> 5.7		> 11.4
Albumin	g/L	< 20			
Magnesium	mmol/L	< 0.4	> 1.23	< 0.3	> 3.3

Definition of Potentially Clinically Significant Laboratory Values

Laboratory values will be considered as potentially clinically significant if they are Grade 3 or higher as shown in [Table 4](#) and [Table 5](#), with the following exceptions:

- GGT: Grade 4
- Total bilirubin: $> 2 \times \text{ULN}$
- Concurrent ALT or AST $> 3 \times \text{ULN}$ and total bilirubin $\geq 2 \times \text{ULN}$

- Concurrent ALT or AST $> 3 \times \text{ULN}$, ALP $< 2 \times \text{ULN}$ and total bilirubin $\geq 2 \times \text{ULN}$

The maximum ratio relative to the ULN will be used to determine if subjects met the criteria listed above. The ALT, AST, and total bilirubin values need to be concurrent (i.e., collected on same date) and should be collected within 49 days following the last dose date of any study drug in order to meet the defined criteria.

